Effects of Mindfulness Meditation on Trait Mindfulness, Perceived Stress, Emotion Regulation, and Quality of Life in Hemodialysis Patients: A Randomized Controlled Trial

Study Protocol

Document Date: October 29, 2020

NCT number: Not yet issued

Introduction

End-stage renal disease (ESRD) has been reported to be a major cause of disability and increased mortality worldwide. In patients with ESRD, hemodialysis is a critically vital therapy that prolongs survival and improves quality of life through the excretion or removal of poisonous metabolic waste from the human body (1). However, compliance with treatment has been found to be poor among ESRD patients (2). Such incompliance can be attributed to the different sources of stress associated with hemodialysis, including hemodialysis complications, time-consuming treatment schedules, restriction of dietary and fluid intake, and prescription of multiple medications (3, 4). These sources of stress, in addition to the signs and symptoms of ESRD, result in diminished health-related quality of life, which is associated with increased risks of morbidity, mortality, and incompliance with hemodialysis therapy (3, 5).

Despite the significant physical, emotional, and social burdens of stress, stress-reduction strategies have been inadequately used in patients undergoing hemodialysis. This may be contributed to the small-scale studies on psychotherapies with variable and holistic outcomes and the limited availability of evidenced-based coping interventions that are significantly supported (6). Mind-body therapies, which comprise a variety of techniques that increase the capacity of the mind to influence the functions of the body using emotional strategies, have gained increasing popularity worldwide in recent years. Evidence shows that mind-body therapies are affordable, easily-practiced, and safe, and that they improve perceived stress, health-related outcomes, and quality of life among various community-dwelling and clinical populations (7, 8). One of the most popular mind-body therapies in the literature is mindfulness meditation, which has been found to be a feasible, beneficial, and well-tolerated therapy in hemodialysis patients (6).

It is theoretically claimed that mindfulness meditation can positively impact perceived stress, known also as stress appraisal, and quality of life through the improvement of trait mindfulness and emotion regulation (9). Hemodialysis is appraised as an uncontrollable, threatening situation, since hemodialysis patients must undergo hemodialysis for their entire lives for survival. Therefore, hemodialysis is not a cure for terminal renal diseases but rather a maintenance therapy (10). It is claimed that repeated mindfulness-based practices cultivate and improve the natural mental capacity of mindfulness, called trait mindfulness (9). Trait mindfulness is described as the mental capacity to pay attention to, be aware of, and accept current experiences in a non-judgmental way (11). This developed mental capacity enables psychological distance through a process of decentered attention, through which one's attention (e.g., thoughts, emotions, and sensations) shifts from the contents of consciousness to the process of consciousness itself. In turn, this can help to stop initial automatic uncontrollable appraisals and broaden attention and awareness to include previously overlooked positive aspects of self, context, or events. Based on this new information, it becomes possible to flexibly select adaptive responses and to reappraise events as beneficial or meaningful (i.e., positive reappraisals). Trait mindfulness also enables individuals to acknowledge and accept their current experiences, even if these experiences are uncomfortable. In addition, trait mindfulness helps individuals to not engage in judgmental or negative thinking or avoidance of these experiences, resulting in less reactivity to stressful situations and increased quality of life (9, 10).

Research supports these theoretical claims, whereby mindfulness meditation has been found to be highly effective for a variety of health outcomes in several psychiatric and medical illnesses (8, 12). For patients undergoing hemodialysis specifically, few studies have demonstrated that mindfulness meditation significantly improves trait

mindfulness (13, 14), stress symptoms (14, 15), emotion regulation (16), and quality of life and general health (15, 17) in Western and Asian countries. However, no study has examined the effectiveness of mindfulness-based interventions among ESRD patients undergoing hemodialysis in the Arab countries such as Kuwait. Therefore, any generalization of these previous study findings to other hemodialysis patients of different cultures such as ESRD patients in Kuwait is limited due to the different belief systems and self-care practices of these cultures. Thus, the current study aimed to examine the effects of a mindfulness-based intervention on trait mindfulness, perceived stress, emotion regulation, and health-related quality of life in ESRD patients undergoing hemodialysis in Kuwait.

Theoretically, investigating the effects of mindfulness meditation on the selected variables may provide insight into the mechanisms through which mindfulness meditation impacts quality of life in hemodialysis patients. The current study findings may enrich the body of knowledge on mindfulness meditation and bridge the gap in the literature regarding the effects of mindfulness meditation on patients receiving hemodialysis. Practically, the findings of the present study may guide decision-makers in adopting mindfulness meditation in Kuwaiti hospitals.

Methods

Design

This study used a repeated-measures, randomized, wait-list, control design and was conducted between January 2021 and May 2021 in the dialysis center at Jahra Hospital, Kuwait. Seventy-four ESRD patients undergoing hemodialysis were recruited using convenience sampling. Jahra Hospital is a governmental hospital with one of the biggest dialysis centers in Kuwait, with a female ward, male ward, and isolation ward. The center holds 70 dialysis machines/beds, with an average number of 30 patients managed per day.

The inclusion criteria for participation in this study were being a patient with ESRD undergoing hemodialysis three times a week, being aged 18 years old or over, and being able to read and write in Arabic. The exclusion criteria included being a patient with cognitive dysfunction or mental retardation, taking psychopharmacological drugs, or undergoing psychotherapy. A research assistant, who was not involved in the recruitment or patient assessment processes, randomly assigned the participants to the intervention group (n=37) or the control group (n=37) using a simple 1:1 computer-generated sequence. The trial is reported in accordance with the CONSORT guideline.

Determination of the Sample Size

The required sample size was calculated using G-power version (3.1). Given a mixed-design (within groups and between groups) repeated measures ANOVA, power of 0.95, moderate effect size of 0.25, and α of .0125, the required sample size was 56 subjects. A P-value of 0.0125 was set as the significance level for the main analysis tests. The p-value was adjusted due to multiple testing by dividing the p-value of .05 by 4 (number of dependent variables). In a similar study, an attrition rate of 30% and a non-attendance rate of 30% (excluding dropouts) were estimated (18). Thus, taking into consideration of 60% attrition and nonattendance rates, the final total sample size was 89 patients.

Data Collection Instruments

The study data were collected using an Arabic self-report questionnaire with five parts:

Demographic characteristics. This section included a question for each following variable: Age, gender, employment status, nationality, family status, and educational levels.

Trait mindfulness. Mindfulness is defined as open or receptive awareness of and attention to what is taking place in the present (19). An Arabic version of the Mindful Attention Awareness Scale (MAAS) was used to measure trait mindfulness (20). The MAAS is one-dimensional and comprises 15 items measured on a six-point Likert-type scale ranging from 1 (almost always) to 6 (almost never). The score range is between 15 and 90, with higher scores indicating higher levels of trait mindfulness. The original scale has shown strong psychometric properties when validated among college students. The scale showed single-factor construct and a Chronbach's alpha of 0.82 among a sample of university students (19). Correlational, quasi-experimental, and laboratory studies have shown that the MAAS taps a unique quality of consciousness that is related to, and predictive of, a variety of self-regulation and well-being constructs (19). The Arabic MAAS has been shown to have excellent internal consistency and convergent validity among an Arab population (20). In our study, the Chronbach's alpha values for the MAAS was 0.93.

Perceived stress. The Arabic version of the Perceived Stress Scale (PSS) was used to measure the degree to which situations in one's life are appraised as stressful (unpredictable, uncontrollable, or overloaded) (21). The scale comprises 10 items which are measured on a 5-point Likert scale (0=never, 4= very often) and which are relatively free of content specific to any subpopulation group. The total possible score ranges from 0 to 40, with higher scores indicating higher levels of perceived stress (stress appraisal) (22). The PSS has been validated for use among college students. The internal consistency coefficient for the PSS is .84 and the scale's test-retest reliability is .85 (22). The Arabic PSS has been shown to have adequate reliability and validity and is considered a suitable instrument for assessing perceived stress in Arab people (21]. the Chronbach's alpha values for the PSS was 0.82.

Emotion regulation. Emotion regulation is defined as the processes by which individuals influence which emotions they have and how they experience and express these emotions (24). The Arabic version of the Emotion Regulation Questionnaire (ERQ) was used to assess emotion regulation among the study sample (23). The questionnaire items are scored on a 7-point Likert-type scale ranging from 1 (strongly disagree) to 7 (strongly agree) and are divided into two subscales, namely cognitive reappraisal and expressive suppression. Higher scores indicate greater emotion regulation abilities (24). The Arabic version of the ERQ has shown valid and reliable results among the Arab population (23). In our study, the Chronbach's alpha values for the ERQ was 0.81.

kidney disease-quality of life. The Arabic version of the kidney disease-Quality of Life questionnaire (KDQOL-36) is used to assess kidney disease-related quality of life and consists of four subscales: Generic Core (Physical Component Summary (PCS, 12 items) and Mental Component Summary (MCS, 12 items)); Symptoms/Problems (12 items); Burden of Kidney Disease (4 items), and Effects of Kidney Disease (8 items) (25). The scores of the different subscales are calculated according to the KDQOL-36 scoring system. Raw, pre-coded numeric values for each item are transformed linearly to a range of 0 to 100, with higher scores reflecting better kidney disease-quality of life (26). The Arabic version used in this study showed good psychometric qualities among Arab patients with chronic renal failure (25). In our study, the Chronbach's alpha values for KDQOL-36 was 0.93.

Intervention

The experimental group received the Smith's version of mindfulness meditation (27), which is a standardized theory-based intervention found to be effective in improving stress and its related health problems. The Smith's version of mindfulness meditation (27) comprises the following components:

1. Being mindful of breathing, which includes easily taking in a full, deep breath, filling the lungs, simply exhaling, and then breathing naturally. It also includes noticing and simply attending to the air as it flows in and out of the nose and moves deeper into the throat and lungs (5 minutes).
2. Being mindful of the body, which includes attending to how the body feels from head to toes and noticing any sensations that come and go. Upon noticing a sensation, the individual must gently note it, let it go, and continue attending to how the body feels (5 minutes).
3. Being mindful of thought, which includes attending to the mind as thoughts come and go. Whenever a thought or feeling comes to mind, the individual should just notice it, let it go, and continue attending to the mind repeatedly (5 minutes).
4. Being mindful of sounds, which includes attending to the sounds one hears, without thinking about them. The individual must gently notice the sound, let it go, and continue waiting (5 minutes).
5. Being mindful of taste, which includes imagining a wonderful bowl of pieces of one's favorite fruit and simply attending to a taste sensation, without thought, analysis, or effort (5 minutes)
6. Full meditation, which includes gently opening one's eyes and being mindful of the world of the moment, quietly attending, and waiting. When noticing something, be it a sight, sound, thought, or sensation, the individual must let it go and then resume attending, doing nothing else, and waiting for what comes next (5 minutes).

The experimental group received 30-minute individually administered, guided, chairside interventions during their hemodialysis sessions. This protocol has been found to

be feasible and effective for patients undergoing hemodialysis (6). Smith (2005) explained in his ABC relaxation theory that at least two and preferably five weekly 30-minute sessions of actual training of mind-body therapies should be provided to evoke relaxation, relieve stress, and improve health in general populations. However, for hemodialysis patients, it has been suggested that brief program formatting with at least 400 total minutes may lead to greater health benefits (18). Accordingly, the experimental group received 30-minute mindfulness meditation sessions 3 times a week for 5 weeks (450 minutes)

The participants also received a 2-hour foundation course which was introduced and supervised by one of the study researchers prior to the actual training sessions and which taught the participants the intervention basics, benefits, protocol, and method of access. To ensure the consistent delivery of the intervention, the researcher recorded the intervention instructions in Arabic based on the Smith (2005) protocol and sent the audio-recorded instructions to the participants via WhatsApp or email. The audio-recorded intervention contents were validated by 2 psychologists and experts in meditation. The recorded intervention instructions were accessed by the participants during the sessions using their cell phones and headsets, as recommended (18). This method allowed for up to 3-5 participants to listen to the instructions and perform the intervention simultaneously.

The researcher who was responsible for developing the study intervention and supervising the intervention delivery was an experienced mind-body practitioner who had received a 4-day training course on mindfulness meditation. The researcher attended the sessions to manage any potential interruptions and evaluate the intervention delivery. The participants' privacy was maintained using curtains surrounding each participant during the intervention. The participants were asked not to share any information related to the intervention with the participants in the control group.

The participants in the control group were instructed to sit with their eyes closed and relaxed for 30 minutes 3 times a week for 5 weeks during hemodialysis sessions to control for the nonspecific effects of social interaction and environment (35). The timings of the control group sessions were similar to those of the experimental group, whereby if a given experimental group intervention lasted for 30 minutes, the control group participants would be asked to sit with their eyes closed and relax for 30 minutes also.

Procedure

First, the permission from the instruments used in the study was obtained. Recruitment of participants was conducted by one of the study researchers after obtaining approval to conduct the study from the hospital administrators. The study purposes and protocol were explained to the patients in detail. Patients who agreed to participate in the study and met the eligibility criteria were asked to sign a consent form, and the participating patients were then randomly assigned to the two study groups. The baseline measurements of the study variables were taken using the self-report questionnaires, which were administered by a research assistant who was not involved in any other parts of the study. The study variables were also measured two weeks post the start of the intervention and at the end of the final session for both groups under the same conditions. All measurements were privately taken at the dialysis center.

Data Analysis

SPSS version 25 (SPSS Inc., Chicago, Illinois, USA) was used to analyze the collected data. Prior to the main analysis, outliers and missing data were examined and managed as appropriate. Then, the assumptions of the statistical tests used, normality using histogram graph, homogeneity of variance, and sphericity were checked and managed as appropriate. Mauchly's test of sphericity is used to assess whether the sphericity assumption has been violated. When Mauchly's test of sphericity was significant ($p < .05$),

the degrees of freedom were corrected using Greenhouse-Geisser estimates of sphericity. The comparability of the two groups was evaluated in terms of demographic characteristics and the baseline measurements of the dependent variables using t-test and Chi square, based on the measurements of the dependent variables. The main analysis was conducted with repeated-measures ANOVA (mixed design: within and between groups). A P-value of 0.0125 was set as the significance level for the main analysis tests. The p-value was adjusted due to multiple testing by dividing the p-value of .05 by 4 (number of dependent variables).

Ethical Considerations

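### The sample-size section arrives at 89 patients, but the Design section recruits and randomises 74, and nothing reconciles the two; the allowance for loss built into 89 is not delivered

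*Combined protocol and SAP*

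**What the plan says.** All the relevant text is in the Methods of the combined protocol and SAP.

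- **Determination of the Sample Size.** For a mixed-design repeated-measures ANOVA with effect size 0.25, alpha 0.0125 and power 0.95, "the required sample size was 56 subjects". From a similar study, "an attrition rate of 30% and a non-attendance rate of 30% (excluding dropouts) were estimated". The two rates are added to 60%, and the section ends: "the final total sample size was 89 patients".
- **Design.** "Seventy-four ESRD patients undergoing hemodialysis were recruited using convenience sampling". A research assistant then "randomly assigned the participants to the intervention group (n=37) or the control group (n=37"), which again makes 74.
- **Procedure.** Besides baseline, outcomes are "measured two weeks post the start of the intervention and at the end of the final session", so there are three measurements.

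Neither Procedure nor Data Analysis mentions 89 or 74. No section says that recruitment fell short, that 74 replaced 89, or why the numbers differ.

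**The concern.** One Methods chapter gives two sizes for the same trial, both in the past tense and without a link between them. The 56 is the number needed in the analysis, and 89 is the only figure that carries the plan's stated allowance for loss. A reader who takes that allowance as in force will credit the trial with a margin that 74 randomised patients do not provide.

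At stake is whether the 0.95 power statement, which is correct for 56 analysed patients, can still be expected to hold once patients are lost at a rate the plan itself considers realistic.

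**Working it through.** **Inputs from the document:** required 56; final total 89; randomised 37 + 37; attrition 30%; non-attendance 30% among those who do not drop out; f = 0.25; alpha = 0.0125; two groups; three measurements. **Not in the document, so assumed:** the correlation between repeated measurements (rho) and sphericity (epsilon = 1).

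**1. Reproduce 56.** For the group-by-time interaction with k = 2 groups and m = 3 measurements:

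- lambda = f² × N × m / (1 − rho), df1 = (k − 1)(m − 1), df2 = (N − k)(m − 1).
- At N = 56 and rho = 0.5: lambda = 0.0625 × 56 × 3 / 0.5 = 21.0, df1 = 2, df2 = 108, power 0.952.
- At N = 55, power is 0.948. So 56 is the smallest total that reaches 0.95, and the plan's figure reproduces.

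**2. Reproduce 89.** 56 × 1.60 = 89.6, which gives 89 when truncated. The same method does not give 74. With 30% alone, 56 × 1.30 = 72.8 comes near it, but the plan states no such derivation.

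**3. The gap.** 37 + 37 = 74; 89 − 74 = 15; 15 / 89 = 16.9%.

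**4. Loss that each number can bear while keeping 56 analysed.**

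| Randomised | Tolerable loss | Share |
|---|---|---|
| 74 | 74 − 56 = 18 | 18 / 74 = 24.3% |
| 89 | 89 − 56 = 33 | 33 / 89 = 37.1% |

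**5. Apply the plan's own rates.**

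| Loss to analysis | Left of 74 | Left of 89 |
|---|---|---|
| 30% attrition only | 74 × 0.7 = 51.8, about 52 | 89 × 0.7 = 62.3, about 62 |
| 30%, then 30% of the rest | 74 × 0.49 = 36.3, about 36 | 89 × 0.49 = 43.6, about 44 |

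With attrition alone, 74 ends about 4 below 56 and 89 ends about 6 above it. If non-attenders are also left out of the analysis, both end below 56. Steps 3 to 5 need no assumption about the correlation.

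**6. Power by correlation** (formula of step 1, epsilon = 1).

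| rho | 52 analysed (74 less 30%) | 62 analysed (89 less 30%) | 74 analysed (no loss) |
|---|---|---|---|
| 0.3 | 0.80 | 0.88 | 0.94 |
| 0.4 | 0.87 | 0.93 | 0.97 |
| 0.5 | 0.933 | 0.972 | 0.991 |
| 0.6 | 0.98 | 0.99 | 0.999 |

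Only the row for 0.5 matches the plan's 56. The other rows show how far the answer depends on a value that the plan does not state.

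**The case against.** The strongest reply is that the roles of the two numbers are plain from context. The 89 sits under the sample-size heading and follows from 56 and a loss allowance, so it is a planned figure. The 74 are described as recruited and randomised, so they are accrual. The instrument descriptions report Cronbach's alpha values from this study, so the text was written with data in hand. This stands: 89 planned and 74 accrued is the natural reading. What remains is a shortfall that is neither acknowledged nor explained.

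A second reply is that no sum is wrong and that 74 exceeds 56. This also stands. A reader might infer that the trial is underpowered, but the documents do not support that. With no loss, 74 gives power of about 0.99 at the correlation that reproduces 56. At 30% loss the shortfall is about two percentage points (0.933 against 0.95), and it disappears at correlation 0.6. The 30% comes from another study, and this trial's actual loss is not given.

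A third reply is that 89 is not a secure benchmark either. This is right: 89 keeps 56 under the plan's own rates only if non-attenders who complete the questionnaires are analysed, and the plan does not say whether they are. So it would be too strong to say that 89 was sufficient and 74 is not.

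None of these replies supplies the missing link between the two numbers.

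**Conclusion.** The point holds as an internal inconsistency: the final total in the sample-size section is 15 patients (17%) larger than the number the Design section randomises, and nothing reconciles them. The consequence is a smaller margin for loss. The 56 survive in the analysis only if no more than 24% of 74 are lost, and the plan's 30% attrition would leave about 52.

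The effect on power is borderline under the settings that reproduce the plan's 56. Whether power falls below 0.95 rests on a correlation that the plan does not state. The 0.95 for 56 analysed patients is not in dispute. This is a correction of wording of moderate weight, and it does not call the design into question.

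**What to change.** Restate the size in the same way in Design and in Determination of the Sample Size. If the natural reading is right, for example: *The planned total was 89; 74 were randomised (37 per group)*, followed by the reason. If one of the numbers is an error, correct it.

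Keep the 0.95 power statement for 56 and add: *With 74 randomised, the 56 needed for 0.95 power remain only if no more than 18 (24%) are lost to analysis.* If a power figure for 74 is given, state the correlation and sphericity assumptions on which it depends.

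The cost is a few sentences and a slightly less favourable, conditional power statement.

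### Does the sample size of 56 fail because the plan never says which term of the mixed ANOVA it is powered for?

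*Combined protocol and SAP*

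**What the plan says.** Determination of the Sample Size gives the design as "Given a mixed-design (within groups and between groups) repeated measures ANOVA", calculated in G*Power 3.1, with "power of 0.95, moderate effect size of 0.25, and α of .0125, the required sample size was 56 subjects". The alpha is .05 divided by the four dependent variables.

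Data Analysis describes the main analysis as "repeated-measures ANOVA (mixed design: within and between groups" and adds: "A P-value of 0.0125 was set as the significance level for the main analysis tests". No term of the model is named in either section. The correlation between visits, the sphericity value and the number of visits entered in the software are not stated.

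The other relevant facts are these:

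- **Visits.** Under Procedure there is a baseline measurement, and outcomes are then "measured two weeks post the start of the intervention and at the end of the final session", which makes three visits.
- **Arms.** Under Design, a research assistant "randomly assigned the participants to the intervention group (n=37) or the control group (n=37".
- **Control.** Under Intervention, controls are "instructed to sit with their eyes closed and relaxed for 30 minutes 3 times a week for 5 weeks", to allow for nonspecific effects.
- **Aim.** The Introduction states the aim as examining the effects of the mindfulness intervention on the four outcomes.

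**The concern.** A mixed ANOVA with two arms and three visits gives three F tests: group, time and group-by-time. Only the last two can produce 56, and a time test compares no arms. Controls also rest quietly three times a week, so both arms might improve. If both improved equally by 0.53 to 0.61 SD, which is a time f of 0.25, the time test would be significant in about 0.95 of trials, while group-by-time would stay near its nominal 0.0125 (0.012 to 0.014 in simulation). With no deciding term named, a change common to both arms could in principle be presented as the main finding.

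The second worry is the word moderate. An interaction f of 0.25 can correspond to a difference between arms of more than 1 SD at the final session. A reader who took moderate to mean about half an SD would expect more from a null result than the trial could deliver.

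**Working it through.** **Inputs.** From the plan: f = 0.25 (taken as Cohen's f), alpha = 0.0125, target power 0.95, k = 2 arms, m = 3 visits. Not in the plan, so assumed: correlation ρ = 0.5 and sphericity ε = 1.

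**Reproducing 56.** For group-by-time, λ = f²·N·m·ε/(1−ρ), with df (k−1)(m−1)ε and (N−k)(m−1)ε.

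- N = 56: λ = 0.0625 × 56 × 3/0.5 = 21.0; df 2 and 108; power 0.952.
- N = 54: λ = 20.25; df 2 and 104; power 0.943.

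So 56 is the smallest even total that reaches 0.95. For the time test λ is the same and the numerator df is m−1 = 2. With k = 2 this equals (k−1)(m−1), so the two tests cannot be told apart by sample size.

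**Group main effect.** λ = f²·N·m/(1+(m−1)ρ), with df 1 and N−2. At N = 56 and ρ = 0.5, λ = 10.5/2 = 5.25 and power is 0.39; 188 patients would be needed. Even at ρ = 0, λ = 10.5, power is 0.74 and 96 are needed. The group effect is ruled out.

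**How firmly the inputs are identified.** Not firmly. The smallest even N is also 56 with two visits at ρ of about 0.62 to 0.63, with four visits at 0.39 to 0.40, and with three visits, ε = 0.75 and ρ of 0.60 to 0.61.

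**What f = 0.25 means as an interaction.** Take arm differences of 0, a·d and d SD at the three visits (equal baselines). Then f is half the standard deviation of these three values, with divisor 3.

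| Shape | f/d | d for f = 0.25 |
|---|---|---|
| Linear (a = 0.5) | 0.204 | 1.22 SD |
| Step (a = 0 or 1) | 0.236 | 1.06 SD |
| Week-2 difference 1.5 times the final one | 0.312 | 0.80 SD |

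With two visits (0, d), f/d = 0.25 and d is exactly 1.00 SD. A claim that the power applies to more than 1 SD therefore presumes that three visits were entered.

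**Dependence on the true correlation.** This is the final-session difference detectable with 0.95 power (three visits, sphericity), from step to linear onset:

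| ρ | 56 analysed | 74 analysed |
|---|---|---|
| 0.5 | 1.06–1.22 SD | 0.91–1.05 SD |
| 0.7 | 0.82–0.94 SD | 0.71–0.82 SD |
| 0.85 | 0.58–0.67 SD | 0.50–0.58 SD |

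**Could one sentence replace the word moderate?** Not without the sponsor's inputs. If two visits at ρ = 0.625 were entered, three-visit power for f = 0.25 at 56 is 0.99. If four visits at ρ = 0.395 were entered, it is 0.90. In either case, attaching 0.95 to 1.06–1.22 SD would be false.

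**Which term the text points to.** Four features agree. The calculation is set up as mixed within and between, in a trial of two randomised arms. The aim is the effect of the intervention. The resting control is there to remove changes common to both arms, and the interaction is the term that does this. Alpha is split by outcome alone, which fits one deciding test per outcome.

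**The case for a change.** The strongest case for acting is that the text really is silent. The phrase about within and between groups describes a design, not a hypothesis, and the sample size cannot separate group-by-time from time. Naming the term costs a few words. On sensitivity, if the final difference were 0.5 SD (a benchmark that is not in the plan), power with 56 analysed at ρ = 0.5 would be only 0.18 to 0.26, and 0.26 to 0.37 with all 74. Without any correlation assumption, the 95% interval for a final-session difference has a half-width of 0.54 SD with 28 per arm and 0.46 SD with 37 (t·√(2/n)). A null interaction would therefore not exclude a half-SD benefit.

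The silence and the arithmetic stand. What does not follow is that the plan must change. Nothing in it suggests that a time effect would be offered as evidence for the intervention, and a time effect alone would not answer the stated aim. The power figures depend heavily on ρ: for the same 0.5 SD they rise to 0.71–0.85 with 56 and 0.86–0.95 with 74 at ρ = 0.85. The only correlation-like figure in the plan is the PSS test-retest value of .85, for one scale and with no interval given, so it is suggestive only. Confidence intervals for final-session differences would be useful output. How they apply to instruments with several scores, such as the ERQ, which is "divided into two subscales, namely cognitive reappraisal and expressive suppression", is a separate question of outcome definition.

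**Conclusion.** The concern describes a real omission, but it does not call for a change. No stated number is wrong: 56 follows from f = 0.25, alpha .0125 and power 0.95 for a group-by-time test with three visits, ρ = 0.5 and ε = 1. The unnamed term is a gap that an analyst would fill sensibly, because the design, aim, control condition and alpha split all indicate group-by-time. Naming it and listing the software inputs would be a minor clarification; it would alter neither enrolment, conduct nor the analysis as it would naturally be run.

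The sensitivity of 1.06 to 1.22 SD is worth bearing in mind when a null result is read. It holds only for three visits, equal baselines, ρ = 0.5, sphericity and an effect that does not peak and fade. A higher true correlation makes the detectable difference smaller. The later inflation of 56 for attrition is a separate matter and was not assessed here.

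### The step from 56 to 89 multiplies by 1.6 instead of dividing by the retained fraction, and the plan does not say whether non-attenders are analysed

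*Combined protocol and SAP*

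**What the plan says.** Methods, Determination of the Sample Size, gives the base requirement as "power of 0.95, moderate effect size of 0.25, and α of .0125, the required sample size was 56 subjects". It then takes two loss rates from a similar study: "an attrition rate of 30% and a non-attendance rate of 30% (excluding dropouts) were estimated (18"). The two are summed, and the section ends: "Thus, taking into consideration of 60% attrition and nonattendance rates, the final total sample size was 89 patients".

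Methods, Design, reports a different number: "Seventy-four ESRD patients undergoing hemodialysis were recruited using convenience sampling". They were allocated 37 to each arm.

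Methods, Procedure, sets two assessments after baseline: "The study variables were also measured two weeks post the start of the intervention and at the end of the final session". On incomplete data, Methods, Data Analysis, says only that "outliers and missing data were examined and managed as appropriate". Neither section defines an analysis set, or says whether a patient who stays in the trial but misses sessions is kept in the analysis.

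**The concern.** An allowance for losses exists so that the number left at the end is still the number the power calculation needs. Multiplying by one plus the loss rate does not achieve that: a 60% loss from 89 leaves fewer than 36 patients, not 56. The gap between multiplying and dividing is small for small losses but large at 60%.

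What is at stake is the 0.95 power claim, which the plan attaches to 56 analysed patients. How far it is affected depends on whether non-attendance removes a patient from the analysis. The plan's use of 60% implies that it does, but nothing in the analysis section confirms this.

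**Working it through.** **Inputs.** From the sample size section: 56 patients, f = 0.25, alpha 0.0125 (0.05/4), power 0.95, attrition 30%, non-attendance 30%, combined 60%, final size 89. From Design: 74 randomised, 37 + 37. From Procedure: three measurements (baseline plus two). Assumed, because the documents do not state them: correlation between measurements 0.5 and epsilon 1.

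**Step 1. Reproduce 56.** For the group-by-time interaction with 2 groups and 3 measurements, the noncentrality is λ = f² × N × 3/(1 − 0.5). At N = 56, λ = 0.0625 × 56 × 3/0.5 = 21, with 2 and 108 degrees of freedom. Power is 0.952; at N = 54 it is 0.943. So 56 is the smallest size with equal arms under these settings. With epsilon 1, correlations of 0.4 and 0.6 would give 68 and 46, so the plan's own 56 points to a correlation close to 0.5.

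**Step 2. Reproduce 89.** 56 × 1.60 = 89.6, truncated to 89. The other routes tried do not give it: 56/0.70 = 80; 56/0.49 = 114.3; 56/0.40 = 140; 56 × 1.3 = 72.8; 56 × 1.3 × 1.3 = 94.6.

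**Step 3. Largest loss that still leaves 56.** From 89: 1 − 56/89 = 37.1%. From 74: 1 − 56/74 = 24.3%, which is less than the 30% attrition alone.

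**Step 4. Size needed, evaluable number and power under each reading.** The retained fraction is 0.70 if only attrition removes patients. It is 0.70 × 0.70 = 0.49 if non-attendance is 30% of those who stay, and 1 − 0.60 = 0.40 if the rates are added. The size needed is 56 divided by that fraction.

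| Reading | Retained | Needed to keep 56 | Left from 89 | Power | Left from 74 | Power |
|---|---|---|---|---|---|---|
| Attrition only | 0.70 | 80 | 62.3 | 0.972 | 51.8 | 0.927 |
| Both, in sequence | 0.49 | 115 (116 for equal arms) | 43.6 | 0.864 | 36.3 | 0.774 |
| Both, added | 0.40 | 140 | 35.6 | 0.758 | 29.6 | 0.645 |

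Power uses the formula of step 1, with the evaluable number rounded down. Rounding up changes little: 0.774 at 36, 0.874 at 44, 0.933 at 52 and 0.666 at 30.

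**Step 5. Sensitivity to the assumptions.** Steps 2 and 3, and the counts in step 4, use neither the correlation nor epsilon. For power, epsilon was varied from 0.5 to 1, each time with a correlation that still returns 56. Power at 35 patients stayed at about 0.75 to 0.78, and at 43 patients at about 0.86 to 0.88.

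**The case against.** The strongest reply is that non-attendance is a matter of adherence, not of missing outcomes. The plan separates it from dropout. Sessions take place during dialysis, which these patients have three times a week, and the questionnaires are completed at the dialysis center. A patient who skips meditation may well still be there to be assessed, and nothing says such patients are dropped. The non-attendance rate may even be a share of sessions rather than of patients, in which case neither 51% nor 60% is a patient loss. On this view 80 are needed and 89 leaves about 62, with power of about 0.97. The extra allowance could be a margin for diluted exposure.

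This stands as a possibility, and it means the shortfall for 89 is conditional. It does not rescue the sentence. If non-attenders are analysed, their rate should not enter a loss allowance, and the plan offers no dilution argument in its place.

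A second reply is that enrolment appears to be over, since the text is in the past tense and reports scale reliabilities from the study's own data, so 89 no longer governs anything. That is why no added enrolment is asked for; the justification and its power claim remain to be read and relied on. A third is that 74 against 89 is a separate recruitment discrepancy. In part it is, but 74 bears directly on whether 56 is protected: even with attrition alone it leaves about 51. That particular loss is modest, with power of about 0.93 against 0.95.

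**Conclusion.** The concern holds. The figure 89 comes from multiplying 56 by 1.6, and dividing by the retained fraction gives 80, 115 or 140 depending on how the two rates are read. This is plain arithmetic and rests on no assumption.

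The consequence for 89 cannot be determined from the plan. The expected evaluable number is about 62 if non-attenders are analysed, and about 43 or 35 if they are not, with power of about 0.97, 0.86 or 0.76. For the 74 reported as randomised, the expected number is below 56 on every reading: about 51, 36 or 29, with power of about 0.93, 0.77 or 0.65. The power figures apply to the group-by-time interaction with correlation 0.5 and epsilon 1, the settings that return the plan's 56.

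**What to change.** State whether patients who miss sessions stay in the analysis, then correct the sentence in one of two ways.

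- **Option 1.** State that all randomised patients with outcome data are analysed. Inflate for the 30% attrition only (56/0.70 = 80) and delete the 60%.
- **Option 2.** Keep both losses. Say whether they apply in sequence (51%) or are added (60%), give the matching size (115, or 116 for equal arms; or 140), and restate the expected evaluable number and power for 89.

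Under either option, give the expected evaluable number and power for the 74 randomised, and state the correlation and epsilon assumed. If the choice is made after data collection, say so.

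The cost is two or three corrected sentences, with no change to enrolment, alpha or analysis method. The price is candour about power: unless option 1 is adopted, the value for 89 falls below 0.95, and for 74 it does so either way.
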